A Randomized Controlled Trial With Retention Testing to Determine the Most Effective Intervention for
Hemorrhage Control Readiness for Laypersons: The PATTs Trial

January 29, 2018

Study Protocol and Statistical Analysis

a. Study design:

- a. Prospective, randomized, multi-arm, open-label trial with follow-up retention testing

b. Location:

- a. Gillette Stadium, Foxborough, Massachusetts, USA.

c. Consent:

- a. Participation in the study was voluntary and oral consent was obtained from all subjects. A fact sheet was provided to all participants.

d. Inclusion/Exclusion criteria:

- a. Adult (18 years and above) volunteers with no prior hemorrhage control training or experience were included in the trial.
- b. Anyone with previous formal hemorrhage control or tourniquet training was excluded from the trial analysis.

e. Randomization:

1. Eligible study subjects were randomized into the following arms using block randomization such that for every four participants, one was randomized to each of the four arms:

- i. **Control arm:** Study subjects in this arm of trial received no intervention (no training or access to point-of-care prompts) to assess baseline competence in hemorrhage control.
- ii. **Experimental arm 1:** Study subjects in this arm were given the American College of Surgeons Bleeding Control Basic (B-Con) in-person training course by qualified instructors. This curriculum was developed by a collaboration between American College of Surgeons and the Hartford Consensus.⁹ The session included a multimedia presentation in a class format that included some background information about extremity hemorrhage and potential benefits of immediate first-response and hemorrhage control, steps to take in a mass casualty scenario and instructional videos on hemorrhage control modalities and their appropriate use. This was followed by hands on training in hemorrhage control, with 1:4, instructor to trainee ratio.
- iii. **Experimental arm 2:** Study subjects in this arm received a commercially available audio bleeding control kit. The kit included diagram and visual aids to identify the correct severity of injury and determine the appropriate method of bleeding control. The kit also had buttons on it to play stepwise audio instructions on application of compression dressing, hemostatic packing and tourniquet application in two languages (English and Spanish). The audio kits were bought at market price and the name of the manufacturer was not mentioned in the manuscript to avoid conflict of interest.
- iv. **Experimental arm 3:** Study participants in this arm of the trial received bleeding control flashcards that contain diagrams and figures to correctly identify the severity of injury and visual instructions on appropriate application of pressure dressing, hemostatic packing and tourniquet.

f. Sample size calculation:

- a. Sample Size calculation was done using Stata v14.1 with 80% power and an alpha level of 0.05. Trial arm paired-comparisons were taken as independent trials and sample size was calculated for each pair. The largest number was taken as the sample size for each arm. The smallest difference in application rate, and the arm used to determine sample size calculation, was between the control and flashcard arm.
 - i. Control group expected application rate 20% based on prior studies
 - ii. Flashcard Proportion expected application rate 44% based on prior studies
- b. Final sample size is 412 with 103 subjects in each arm. This is before exclusion of individuals with prior hemorrhage control training thus, to account for 20% of individuals to report prior training, over 125 individuals will be recruited to each arm.

g. Pre-study questionnaire:

- a. Study subjects were given a pre-trial questionnaire to gather information regarding age, gender, level of education, any prior first-aid training, and if they reported prior first-aid training, whether it included hemorrhage control training. Those individuals who reported prior hemorrhage control training were then asked an open ended question about what that training consisted of. The questionnaire also included questions to determine participants willingness to assist in an emergency and self-reported comfort level in acting as a first-responder in a mass causality scenario. Answers were presented on a Likert-type scale.

h. Post-trial questionnaire:

- a. After the hemorrhage control test, all participants were given a post-trial questionnaire which assessed their perception of usefulness of the training, willingness and self-reported comfort-level in providing first response in a mass causality scenario on a Likert-type scale.
- b. Questionnaires will also be re-administered at 3-9 month retention testing, which will assess participant perception of usefulness of the training, self-reported willingness and comfort-level in providing first response in a mass causality scenario on a Likert-type scale as well as other questions relating to emergency preparedness and hemorrhage control.

i. Protocol:

- a. A reviewer will read aloud a simulated scenario describing an explosion in a public gathering. A bleeding mannequin with traumatic amputation of leg just above the knee will be present. The participant will then be directed to a nearby bleed-control box and asked to stop the bleeding. The bleed-control box will contain a combat application tourniquet (CAT). The reviewer will start timing after directing the subject to the bleed-control box.

Subjects in the control arm were directly subjected to the bleeding control test. Experimental arm 1 subjects will attend B-Con course taught by ACS trained instructors and then subjected to the test. Experimental arm 3 and 4 subjects received an audio guide and flash card in their bleed-control box respectively,

during the test. At retention testing, participants were not retrained nor had available point of care prompts.

The participants were timed until they feel that they had stopped the bleeding. Time for complete bleeding control and tourniquet application was recorded only for subject who appropriately control the hemorrhage within 7 minutes. Appropriateness of hemorrhage control was determined by correct placements of tourniquet and adequate pressure of the tourniquet as determined by attempting to forcefully slide a Kelly clamp under between the tourniquet and the extremity of the mannequin. For unsuccessful hemorrhage control, the reason for failure was recorded. No feedback was given to the participant during the test.

- b. 20 reviewers were used for the purpose of this study. All the reviewers were physicians, nurses, and EMTs, trained in hemorrhage-control.
1. After testing of the two point of care prompt arms and the control arm, these individuals then underwent the ACS B-Con training from qualified instructors. This training was 45 to 60 minutes long, consisting of an audio-visual presentation with tourniquet application instructions followed by hand-on training under the supervision of an instructor, the same as the B-Con intervention arm.
2. ***Test for retention:***
 - a. 3-9 months after the trial, we planned to test all study subjects with a simulated mass causality scenario for retention of knowledge and skills. This test will be the same as the initial test for competence at tourniquet placement in the trial and the same evaluation form will be used to evaluate the study subjects.

j. Donation of study material:

- a. At the end of the retention study, the bleeding control boxes will be donated to the stadium, to be co-located with AEDs.

1) ***Statistical analysis:***

- a) The primary outcome in our study was the correct application of tourniquets. The main analyses in the randomized study were the pairwise comparisons of the proportion of correct tourniquet application in each of the three intervention arms to the control arm.
- b) In the initial testing phase, the proportion of participants who correctly applied a tourniquet in the three intervention arms were compared to control using three pairwise two-sided Fisher's Exact Test of the three interventions to control in an intent-to-treat analysis (as randomized).
- c) To analyze retention, we performed two pairwise comparisons: 1) all participants tested at retention versus initial control to identify long-term efficacy (correct tourniquet application) compared to no training; 2) participants tested at retention versus initial testing in B-Con randomized arm to identify if there is a significant skill decay 3-9 month after training. Generalized estimating equations z-tests were used in these pairwise tests to account for the repeated measures on participants who were in both the initial and retention phases.
- d) At retention testing, an a priori planned logistic regression analysis was performed to identify any demographic associations with correct tourniquet application between 3 and 9 months after B-Con training. It also assessed for different effects due to the original (randomized) arm in initial testing in case the combination of randomized arm and then

B-con training had differential effects on correct tourniquet application (although our a priori hypothesis was that there would be no difference). Age was divided into categorical variables creating three groups using previously defined age breaks: young adult [18-35 years old (yo)], middle aged adult (35-55 yo), and older adult (> 55 yo). This model assessed for an association between days since training to retention testing, allowing for a non-linear effect. We assessed for co-linearity, and interactions between variables [age and education, age and sex, age and prior training, sex and education, sex and prior training] and ran diagnostics on the model fit. We used Hosmer and Lemeshow's goodness-of-fit test to evaluate our model.

- e) The Wilcoxon rank sum test was used to compare time to correct tourniquet application across arms (restricted to participants in each arm who correctly applied the tourniquet). Demographic variables for each intervention arm versus control and retention versus control were compared using Wilcoxon rank sum tests for continuous variables and two-sided Fisher Exact tests for categorical variables.
- f) The data on empowerment will be analyzed using descriptive statistics. Likert type data will be analyzed using non-parametric tests (Wilcoxon sign rank, Kruskal-wallis test). Single group repeated measures analysis will be used to analyze the change in empowerment over time. The Likert type data will also further be analyzed by transforming it into dichotomous categorical data with those reporting being very likely or very comfortable being a positive response and anything less than that being recorded as a negative. The various empowerment parameters will be assessed for their relationship with skill efficacy (correct tourniquet application).

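### Fixed blocks of four in a single-site open-label trial, with no concealment described, leave a route to selection bias in the comparisons with control

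*Combined protocol and SAP*

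**What the plan says.** Section a (Study design) describes a "Prospective, randomized, multi-arm, open-label trial with follow-up retention testing", and section b gives one location, "Gillette Stadium, Foxborough, Massachusetts, USA". Section e (Randomization) says that eligible subjects were allocated "using block randomization such that for every four participants, one was randomized to each of the four arms". That is a permuted block of four with one slot per arm, and no variation in block size is mentioned.

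The arms are recognisable on sight: a class, an audio kit, a flashcard, or nothing. The Statistical analysis section, items a and b, makes the three comparisons of an intervention arm with control the main analysis, as randomized.

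On eligibility, section e speaks of eligible subjects being randomized, but section d says "Anyone with previous formal hemorrhage control or tourniquet training was excluded from the trial analysis". Section f allows for 20% of recruits reporting prior training. Section g collects that information by self-report, with an open-ended follow-up question. The documents do not say whether the eligibility decision comes before or after the arm is known. They also do not say who generated or held the list, who enrolled, what enrolling staff could see, or whether people were allocated singly or four at a time.

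**The concern.** Random allocation protects a comparison only if nobody who influences entry can foresee the next arm. When the block length equals the number of arms and past allocations are visible, each allocation narrows what can follow, and the last slot of each block is fully determined. Keeping the list in a sealed file does not prevent this, because the inference uses only the rule and the arms already seen.

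The lever would be a choice about who takes the next slot. Staff could call one waiting volunteer before another, or judge a borderline report of prior training one way or the other. If people expected to do well were directed towards intervention slots and others towards control, all three primary differences would be inflated together. Fisher's exact test as planned would neither detect nor correct this.

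**Working it through.** The plan gives no figure for predictability, so there is none to reproduce.

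**Inputs**
- Block of four, one slot per arm: section e.
- Open-label, one location: sections a and b.
- Planned rates: "Control group expected application rate 20% based on prior studies" and "Flashcard Proportion expected application rate 44% based on prior studies" (section f), so the planned effect is 44 − 20 = 24 points.
- "Final sample size is 412 with 103 subjects in each arm" (section f), that is, 103 blocks of four.
- d, the difference in success probability between the stronger and weaker volunteers who could be steered. The documents give no figure. I assume a range of 10 to 20 points.
- Behavioural assumption: allocation is one at a time, and someone who knows the block rule sees earlier allocations and can influence who comes next.

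**1. Predictability of the arm.** The chance of a correct best guess at positions 1 to 4 is 1/4, 1/3, 1/2 and 1. The mean is (0.250 + 0.333 + 0.500 + 1)/4 = 0.521, against 0.25 by chance. The fourth slot is certain, so 1/4 of allocations (103 of 412) are known beforehand.

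**2. Predictability of control versus intervention.** Control is equally likely to fall at any of the four positions. The slots after it are all known to be intervention slots: (3 + 2 + 1 + 0)/4 = 1.5 per block on average. If control has not appeared by position 4, that slot is known to be control: 0.25 per block on average. The total is 1.75/4 = 43.75% of allocations.

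**3. Worst-case shift, fixed blocks.** Take one intervention arm T against control C. Until either appears in a block, they are equally likely to be next. Once one has appeared, the other is known to be still to come. The steerer offers stronger volunteers (+d/2) while T is outstanding and weaker ones (−d/2) while C is outstanding. In half the blocks C comes first and T gains d/2. In the other half T comes first and C loses d/2. The mean shift is +d/4 in T and −d/4 in C, so the difference shifts by 0.50d.

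All three comparisons can be shifted at once. Weaker volunteers are offered until control is drawn and stronger ones afterwards. Control then always gets −d/2. Each intervention slot follows control half the time and averages 0. The shift is again 0.50d.

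**4. Randomly varied blocks of 4, 8 and 12.** I simulated runs of about 412 allocations with an observer who knows the set of sizes and updates on every allocation. About 3.5% of allocations are certain (3.4% to 3.7% across runs), best-guess accuracy is about 46%, and the worst-case shift for one comparison is about 0.40d. The reduction in shift is (0.50 − 0.40)/0.50, or about one fifth.

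**5. In points**

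| d (assumed) | Fixed blocks of 4 | Varied 4, 8, 12 | Planned effect |
|---|---|---|---|
| 10 points | 5 | about 4 | 24 |
| 20 points | 10 | about 8 | 24 |

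As an illustration of what such shifts do, take 103 per arm and a true rate of 20% in both arms. The two-sided Fisher test then rejects 3.3% of the time without bias. With a spurious difference of 5 points, split equally between the arms, it rejects 10.9% of the time, and with 10 points 37.0%. These are upper bounds from complete and consistent steering, not forecasts.

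**The case against.** The strongest reply is that predictability is conditional. It needs one-by-one allocation, an observer who knows the rule and tracks the block, and influence over the next slot. The documents describe none of these. The wording of section e also fits four people being taken together and distributed among the arms at once, in which case nothing could be foreseen. A reader might infer that a quarter of allocations were in fact known beforehand, or that the results were biased. The documents do not support that inference, and this part of the objection stands in full.

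Other parts also have weight:
- Staff would have to judge which untrained laypersons could apply a tourniquet, and nothing in the documents supports a particular value of d.
- Volunteers have less reason to hold out for a given arm, because the control and prompt arms receive the same B-Con training after their test (section i, item 1).
- The baseline comparisons in item e of the Statistical analysis section could show gross selection on measured factors, though not on aptitude or motivation.
- Varied blocks alone lower guess accuracy only from 52% to about 46%.

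What the objection does not do is point to a safeguard in the text. The rule as written is the most predictable block design available for four arms, and a better one costs almost nothing.

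**Conclusion.** The point holds as a correctable weakness in the allocation procedure. Its size, if allocation is sequential and visible to enrolling staff, is 25% of allocations certain, 52% best-guess accuracy, and control status known for about 44%. The worst-case shift in an arm-versus-control difference is 0.50d, which is 5 to 10 points on the assumed d of 10 to 20 points.

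The percentages follow exactly from the block rule. The shift in points rests on an assumed d and on perfect steering. If each four was fixed as a group before allocation, or enrolling staff could not see earlier allocations, the route closes.

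It would also be wrong to conclude that varying the block size settles the matter. About four fifths of the worst-case shift would remain, so fixing eligibility before the arm is revealed matters at least as much.

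**What to change.** If allocation is still to take place:
1. Record the pre-study questionnaire and the eligibility decision on prior training before each allocation is revealed, and say so in sections d and e.
2. Keep the list from enrolling staff, and state who generates and holds it.
3. Generate the list with randomly varied, undisclosed block sizes, for example 4, 8 and 12. This cuts certain allocations from 25% to about 3.5%.

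The cost is a new list, a sentence or two of procedure, and a small possible imbalance. With a largest block of 12 (three slots per arm), an unfinished last block can leave final arm sizes differing by up to three.

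Much of the document is in the past tense. If allocation is already complete, the list cannot be changed. The report should then state who enrolled participants, what they could see of earlier allocations, whether each block of four was allocated together, and when eligibility was fixed relative to allocation.

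### The stated 103 per arm does not follow from the stated inputs: 20% versus 44% at 80% power and alpha 0.05 needs 59 to 67, and 103 gives about 95% power

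*Combined protocol and SAP*

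**What the plan says.** Section f (Sample size calculation), item a, sets out the method: "Sample Size calculation was done using Stata v14.1 with 80% power and an alpha level of 0.05". It continues: "Trial arm paired-comparisons were taken as independent trials and sample size was calculated for each pair", and then "The largest number was taken as the sample size for each arm". The pair that sets the size is named: "The smallest difference in application rate, and the arm used to determine sample size calculation, was between the control and flashcard arm". Two rates are given: "Control group expected application rate 20% based on prior studies" and "Flashcard Proportion expected application rate 44% based on prior studies". No rates are given for the in-person course or the audio kit.

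Item b gives the result, "Final sample size is 412 with 103 subjects in each arm", and then the recruitment allowance: "to account for 20% of individuals to report prior training, over 125 individuals will be recruited to each arm".

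The Statistical analysis section, item b, plans the three comparisons with control as two-sided Fisher exact tests. Section e allocates participants equally to the four arms.

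**The concern.** Section f describes a complete chain from inputs to result and states no step between the two rates and 103. A reader who repeats the chain gets a number between 59 and 67. The gap of 36 to 44 per arm is too large for rounding or for the choice between standard formulas.

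At stake is the credibility of a headline design figure. Either 80% is not the power of this design at the stated rates, or one of the stated inputs is not the one that was used. The documents do not say which, so the stated power and the stated size cannot both be cited as they stand.

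**Working it through.** **Inputs.** Control rate p1 = 0.20, flashcard rate p2 = 0.44, power 80% and alpha 0.05 (section f, item a). Equal allocation (section e). Two-sided Fisher exact test (Statistical analysis, item b). Section f does not state sidedness; two-sided is taken from the analysis section. Then z(0.975) = 1.960, z(0.80) = 0.8416, difference 0.24, mean rate 0.32.

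**The plan's figure.** 4 × 103 = 412, so the total agrees with the per-arm number. The question is where 103 comes from.

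**Pooled chi-square.**
n = [z(0.975)·√(2·p̄(1−p̄)) + z(0.80)·√(p1(1−p1) + p2(1−p2))]² / (p2−p1)²
- First term: 1.960 × √(2 × 0.32 × 0.68) = 1.2930
- Second term: 0.8416 × √(0.16 + 0.2464) = 0.5365
- n = (1.8295)² / 0.0576 = 58.11, so **59 per arm**

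**With continuity correction.**
n' = (n/4)·[1 + √(1 + 4/(n·|p2−p1|))]² = (58.11/4) × [1 + √(1 + 4/13.946)]² = 66.18, so **67 per arm**

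**Two-sided Fisher exact, by full enumeration.** Power is 0.798 at 65 per arm and 0.807 at 66, so **66 per arm**.

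| Method | Per arm | Four arms | Shortfall from 103 |
|---|---|---|---|
| Pooled | 59 | 236 | 44 |
| Fisher exact | 66 | 264 | 37 |
| Continuity-corrected | 67 | 268 | 36 |

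Other variants move further from 103: unpooled 56, arcsine 58, one-sided 44 to 54.

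**Could another pair have set the size?** Section f says that control versus flashcard, at 24 points, is the smallest difference. For a 24-point gap the requirement is greatest when the rates straddle 50%, that is 38% versus 62%:
- Pooled: (1.3859 + 0.5777)² / 0.0576 = 66.94, so 67
- Continuity-corrected: 75.04, so 76
- Fisher: power first reaches 80% at 73 and stays above it from 78

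A wider gap needs fewer. No pair consistent with section f comes near 103.

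**Could the 20% allowance be inside 103?** Section f adds it after 103. Applied to the calculated numbers it gives 59/0.8 = 73.75 (74) or 67/0.8 = 83.75 (84), still not 103.

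**What 103 does provide.** With 103 analysable per arm, two-sided Fisher power at alpha 0.05 for 20% versus 44% is 0.951. For 20% versus 38% it is 0.781, and for 20% versus 38.5% it is 0.803. So 80% power at 103 goes with a difference of about 18.5 points, not 24.

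**The case against.** The best defence is that 80% is a floor. On that view 103 meets the target comfortably, and planning more than the minimum is not a design error. Retention testing and a logistic regression are also planned, and both benefit from more participants. It is true that the design is not harmed. But section f offers 103 as the output of the calculation, not as a rounded-up or enlarged number, and it does not mention retention. Retention loss alone would have to be about 35% (from 67) to 43% (from 59) to lead to roughly 103, and no such figure appears.

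A reader might also infer stronger things, which the documents do not support:

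- **That alpha was silently split across the three comparisons.** Section f states alpha 0.05 and treats the pairs as independent trials. A three-way split alone would give 78 (pooled) to 86 (corrected), not 103.
- **That the 20% allowance was counted twice.** This depends on guessing how 103 arose. The text applies the allowance once, after 103.
- **That 103 shrinks to about 82 (103 × 0.8) once trained people are excluded.** Item b does describe 103 as the figure before exclusions, but the same sentence goes on to recruit more than 125 per arm for that reason. Read whole, it makes 103 the number meant to remain.
- **That the trial is underpowered.** On the stated inputs the opposite is true.

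Other combinations of power, rates and inflation can be made to land near 103. The documents favour none of them, so none should be offered as the explanation.

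**Conclusion.** The point holds as a minor error in a stated design figure. The stated inputs give 59 to 67 per arm (236 to 268 in total) against 103 (412), and no reading of section f closes the gap. At the stated rates the power with 103 analysable per arm is about 95%, not 80%.

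The error is on the safe side. The planned comparisons, tests and estimates are unchanged.

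The conclusion assumes a two-sided alpha of 0.05 for each comparison, equal arms, and 103 as the analysable number. It is not sensitive to the last of these: at 125 × 0.8 = 100 analysable per arm, Fisher power is still 0.944. How 103 was obtained cannot be established from the documents.

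**What to change.** In section f, do one of the following.

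1. If the original calculation can be recovered, correct the input or add the step that produced 103, so that the stated rates, test, alpha, power and any inflation lead to that number.
2. If it cannot, remove the claim that 103 was derived at 80% power. Say instead that 103 analysable participants per arm give about 95% power for 20% versus 44%, using a two-sided Fisher exact test at alpha 0.05 per comparison, and label this as computed afterwards. Do not choose an input in retrospect to make 103 come out.

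In either case, state plainly that 103 is the number to be analysed after people with prior training have been excluded.

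The cost is a few sentences. No participants are added, and no test or analysis changes.

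### The pre-study questionnaire asks about hemorrhage-control training only after a yes to first-aid training and lists no item on experience, so it can miss people who do not meet the eligibility criteria

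*Combined protocol and SAP*

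**What the plan says.** Section d (Inclusion/Exclusion criteria) has two items that differ in scope. Item a sets the population: adult "volunteers with no prior hemorrhage control training or experience were included in the trial". Item b sets the analysis exclusion: "Anyone with previous formal hemorrhage control or tourniquet training was excluded from the trial analysis". Experience appears in item a only; the word formal appears in item b only.

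Section e (Randomization) states that "Eligible study subjects were randomized into the following arms using block randomization". It does not say how eligibility was established.

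Section g (Pre-study questionnaire), item a, lists age, gender, education, any prior first-aid training and, "if they reported prior first-aid training, whether it included hemorrhage control training". A further question follows for some: "Those individuals who reported prior hemorrhage control training were then asked an open ended question about what that training consisted of". The remaining items concern willingness to help and comfort in acting as a first responder.

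Section f (Sample size calculation), item b, ties the expected exclusions to self-report: "to account for 20% of individuals to report prior training, over 125 individuals will be recruited to each arm".

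**The concern.** Section d asks whether a person has had hemorrhage-control or tourniquet training at all, and whether they have experience. Section g asks a narrower question, of fewer people: whether a first-aid course they have already reported included hemorrhage control. Someone who took a stand-alone bleeding-control class, or learned to use a tourniquet at work, may not think of it as first aid. If that person answers no to the first question, the second is never put. The trial's own B-Con course is a class of this kind. The open-ended item cannot recover such people, because it goes only to those who have already said yes.

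The control arm is where this matters most. It is there to show what untrained laypersons can do. It is also the reference for all three primary comparisons (Statistical analysis, items a and b) and for the first retention contrast (item c). Trained people left in that arm raise its success rate and leave less room for an intervention effect. Item d and its continuation also plan interactions of prior training with age and with sex. If that variable comes from the same question, it is incompletely recorded there too.

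**Working it through.** **1. Routing, case by case**

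- *Hemorrhage control taught within a first-aid course.* First-aid question yes, follow-up asked, person identified.
- *Formal hemorrhage-control or tourniquet training that the person does not count as first aid.* First-aid question no, follow-up never asked. The person fails item a and falls under the item b exclusion, but the listed questions do not reveal it.
- *Experience without training.* No listed question applies. The person fails item a but is not covered by item b, and so would stay in the analysis under item b however the form were worded. This part is a mismatch between items a and b as well as a gap in the form.

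**2. The plan's sample size**

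Inputs from section f: control 20%, flashcard 44%, 80% power, alpha 0.05. The mean rate is 0.32 and the difference 0.24. For a two-sided test without continuity correction:

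n = [1.960 × √(2 × 0.32 × 0.68) + 0.842 × √(0.20 × 0.80 + 0.44 × 0.56)]² / 0.24² = (1.293 + 0.537)² / 0.0576 ≈ 58.1, so 59 per arm.

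With continuity correction it is 67. The stated 103 per arm does not follow from the stated inputs, which is a separate matter. It is relevant here because at 103 per arm the exact power of the planned two-sided Fisher test at 20% versus 44% is 95.1%, well above the 80% intended.

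**3. Effect of missed people**

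Assumptions, none of them in the documents: a share m of each analysed arm is missed, and these people succeed with probability q whatever their arm.

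- Control rate = 0.20(1 − m) + qm
- Flashcard rate = 0.44(1 − m) + qm
- Difference = 0.24(1 − m)

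For a range of m, the plan expects 20 of every 100 recruits to report training, which leaves 80 analysed. If a quarter to a half as many again go unreported, that is 5 to 10 of the 80: 5/80 = 6.25% to 10/80 = 12.5%. The table runs from 5% to 12.5%, with 20% as a stress case and q from 60% to 90%. Power is by exact enumeration of the two-sided Fisher test at 0.05 with 103 per arm.

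| m | Control rate (q = 60% to 90%) | Difference (points) | Fisher power |
|---|---|---|---|
| 0 | 20% | 24.0 | 95.1% |
| 5% | 22.0% to 23.5% | 22.8 | 92.2% to 91.6% |
| 6.25% | 22.5% to 24.4% | 22.5 | 91.3% to 90.6% |
| 10% | 24.0% to 27.0% | 21.6 | 88.3% to 87.4% |
| 12.5% | 25.0% to 28.8% | 21.0 | 86.1% to 85.1% |
| 20% | 28.0% to 34.0% | 19.2 | 78.3% to 76.4% |

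Worked example at m = 12.5%, q = 90%: control = 0.20 × 0.875 + 0.90 × 0.125 = 0.175 + 0.1125 = 28.75%; difference = 0.24 × 0.875 = 21.0 points.

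The power margin comes from the 103. At m = 10%, 80% power with continuity correction would need 85 to 87 per arm (q = 60% to 90%), against 67 with nobody missed. A trial sized at 67 would have felt the dilution.

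**The case against.** The plan never calls this form the screening tool or the sole eligibility check. Section g says it gathers information. Section e says that eligible subjects were randomized, which implies an eligibility decision that the plan does not describe. Section g is also a prose summary and not the form itself; printed examples or a spoken check might close the gap. Whether a person trained elsewhere would answer no to a question about any first-aid training is conjecture. The consequence, in any case, is conservative dilution, with power above the planned 80% throughout the assumed range.

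Much of this stands, and it limits the point in three ways. First, a reader might infer that ineligible people did enter and remain in the primary analysis. The documents show only that this can happen, and give no count or rate. Second, a reader might infer that the randomized comparisons are biased between arms or that the false-positive rate is inflated. Allocation is random, so missed people are balanced in expectation and neither follows. Third, a reader might blame the questionnaire alone for experienced people staying in the analysis. The item b exclusion does not mention experience, so the form is only part of the cause.

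The objection does not remove the routing rule, which is stated in the text. The 20% allowance is for people who report training, and section g is the only place described where such a report is collected. If another check exists, the plan needs to state it.

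**Conclusion.** The point holds as a gap in the described method: the listed questions cannot fully apply section d, and people who do not meet item a, or who fall under item b, can be missed. The main cost is to interpretation. The control proportion may overstate what untrained laypersons can do, by 2 to about 9 points under the assumptions used (20% rising to between 22% and about 29%). Each difference from control is then understated; the planned 24.0 points becomes 22.8 to 21.0.

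Power is a lesser issue. It stays at about 85% to 92% at 103 per arm over that range, and falls below 80% only in the 20% stress case.

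These figures rest on an assumed share missed, an assumed success rate, and equal success of missed people in every arm. If the interventions also helped those people, the dilution would be smaller. The change is worth making because it costs almost nothing and protects the definition of the trial's population, not because a primary conclusion is shown to be at risk.

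**What to change.** Remove the skip pattern. Before randomization, ask every volunteer directly:

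1. whether they have had any hemorrhage-control or tourniquet training, in any setting, with a follow-up on whether it was formal;
2. whether they have any prior experience of hemorrhage control.

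State that eligibility rests on these answers, and describe any other eligibility check in use. Reconcile section d, item a (training or experience) with item b (formal training only), so that one definition governs both entry and analysis. Keep prior first-aid training as a separate covariate question.

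The cost is two questions and a follow-up on an existing form, and slightly more volunteers may be classed as ineligible. If the data are already collected, report the routing as a limitation on the untrained baseline.
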